# 7 Assessment of Safety

## 7.1 Risks and Benefits

This is a low risk, non-invasive study. There are no invasive or painful procedures anticipated.

Foreseeable risks include the potential for psychological distress from responding to the psychological questionnaires, some of which are routinely collected in the clinical setting. In the case where the additional measures collected through REDCap result in any psychological distress, study participants will have access to a Child and Adolescent Health Care Practitioner and study investigators to discuss their distress or aid them in seeking other avenues for mental health support (eg: GP review for mental health care plan where individuals can access free/subsidised sessions with a mental health professional in the community).

It will be explained to the participant that their involvement in the study is entirely voluntary and that they can withdraw from the project at any stage without affecting their relationship with the health professionals or researchers at Perth Children's Hospital. When a participant withdraws a follow-up phone call will be made to ascertain the reason for withdrawal, complete the exit DTSQ and to refer him/her to other services if required.

Benefits to the participant include the following:

- Participants will be able to be involved as consumer advocates for children, adolescents, families and caregivers living with T1D and improved access to diabetes technology.
- Participants may benefit from the reflection that follows answering the types of questions asked in the study.

## 7.2 Safety

Adverse events are unlikely, however if any participant experiences distress, they will be offered the opportunity to not answer questions, or to discontinue their involvement in the study. At all clinical visits a diabetes social worker is available to support families experience high diabetes distress or experiencing other adverse wellbeing.

Participants will have full access to their usual diabetes clinical triage line and diabetes on-call service outside of office hours if they need to discuss diabetes management, or to be referred for psychological assistance as deemed necessary by the clinical team. After hours psychological assistance in the community is available. This information will be provided in hard copy and included will be the contact details needed to access the services.

## 7.3 Adverse events reporting

Given this study involves standard diabetes treatment, and the treatments being used have been used in previous studies and standard clinical care, the risk of Adverse and/or Serious Adverse Events are unlikely in this low risk, non-invasive study. If they do occur, they will be reported to the HREC according to local procedure.

## 7.4 Follow-up of Adverse Events

The type of follow-up required after an adverse event will be determined by the CPI and PI's on the study team according to clinical and/or psychological need.

# 8 Data Management, Statistical Analysis and Record Keeping

## 8.1 Statistics and Interim Analysis

The cohort newly diagnosed with T1D in the 12 months following study start (the contemporary cohort) will be compared to a historical control (the cohort newly diagnosed between March 2022 and March 2023). Routine clinical data for both cohorts will be extracted from WACDD. Descriptive statistics (mean/SD, median/IQR, or frequency/% as appropriate) will be presented for key demographic and clinical measures. The 24-month HbA1c in the contemporary cohort will be compared to the historical control through multivariable regression model adjusting for potential imbalances in clinical/sociodemographic characteristics. The adjusted mean difference along with 95% confidence intervals will be calculated. A sensitivity analysis using an inverse probability of treatment weighted regression based on propensity score will also be conducted.

Interim analyses employing similar models examining HbA1c difference between the cohorts at 6 and 12 months will be conducted. Further exploratory analyses presenting mean HbA1c over various clinical factors (e.g. urban/remote postcode/SEIFA, insurance status, age at diagnosis, timing of HCL commencement, etc) will also be conducted. Subanalysis reviewing mean HbA1c on those commencing on AHCL within 12 weeks from diagnosis will similarly be examined.

Device uptake and attrition will be presented as frequencies and proportions along with 95% confidence intervals. Bivariate predictors of device use at uptake will be presented through simple contingency tables of device use by clinical and sociodemographic factors (Age group ( $\leq 12$  years,  $> 12$  years), gender, socioeconomic indices for areas quintile (lowest quintile, other 4 quintiles), DKA at diagnosis).

Simple descriptive statistics (mean/SD, median/IQR, or frequency/%) will be presented for CGM metrics and psychosocial measures at each of the follow-up points for the contemporary cohort. Where appropriate, mixed models or non-parametric Friedman tests will be conducted to assess within person change over time.

A cost-effectiveness analysis of the new model of care compared to the previous model of care from a health care system perspective will be led by a co-investigator from Monash university with expertise in health economics. The main outcome of interest will be the incremental cost-effectiveness ratio which captures the mean differences in health outcomes and costs. Health outcomes will be measured by quality-adjusted life years (QALYs), calculated from the CHU-9D instrument. Data will be captured during the trial for the intervention (new model of care) group. The comparator (historical cohort) will not have CHU-9D data available as it was not historically captured. Therefore, we will use CHU-9D data collected on children with diabetes from the Longitudinal Study of Australian Children (LSAC) for quality of life in the comparator group. This is suitable given that LSAC data was collected under the previous model of care which exists in most states/territories (with limited access to AHCL). Other outcomes such as the number of significant events (including hospitalisations) averted will also be explored. Costs include the cost to deliver the new model of care, and the cost of health care services used by participants during the time horizon of the trial (including hospitalisations and emergency department attendances) costed using standard Australian unit prices. Standardised economic evaluation techniques including bootstrapping to determine confidence intervals will be employed. The results of our analysis will also be used to do a budget impact analysis to estimate the financial consequences of adopting the new model of care.

Final analysis will occur after the final study participant has completed the 24 month data collection, however interim analyses will occur approximately 6 monthly from initial pump start in the contemporary cohort.

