Therefore, the PCH Diabetes Service has implemented a model of care aligning with international guidelines to commence AHCL therapy in children following the diagnosis of T1D, alongside initiating ACHL in those with an established diagnosis of T1D. In youth with newly diagnosed T1D cared for within our service, the time to AHCL commencement has reduced from a mean of 9.37 months in 2022 (inclusive of 45 individuals to date) to 3.55 months in 2023 (inclusive of 30 individuals to date). However, given ACHL access is limited to restrictive pathways based on financial status or limited philanthropy, there is a significant gap in equitable access of essential AHCL therapy. This is reflected by the above numbers of those starting AHCL in the newly diagnosed period, as this represents approximately one third of the newly diagnosed T1D cohort in a 12 month period at PCH. Currently, individuals unable to access AHCL are initiated and maintained on MDI with access to a CGM. Hence, in an attempt to improve access, the department has acquired funded support to provide pumps for children who do not have access to pumps through the existing pathways.

The overarching goal of this study is to evaluate the new model of care within the diabetes department at PCH which aims to offer AHCL therapy to **all** children with newly diagnosed T1D, regardless of financial status. AHCL will be offered within 12 weeks following diagnosis of T1D, a time frame in keeping with limited studies in this period, for example the CLOuD trial (16) showing improved outcomes when AHCL was started within 6 weeks from diagnosis, as well as expert input from the Diabetes Clinical Service leads regarding realistic timeframes within current clinical pathways. The combination of a clinical pathway aiming for early initiation of AHCL and equitable technology access for all children is an innovative model of care in T1D. Comprehensive evaluation of the glycaemic outcomes, patient reported outcomes, feasibility and cost-effectiveness of the model are essential and hence are the broad aims of the study.

Real-world evaluation of such models of care represent essential first steps toward collecting the evidence required for improving equitable access to diabetes technology for youth with T1D in both Australia and worldwide.

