In the context of independently sourced funds, AHCL will be now offered to all children with T1D within this model of care. As per current model of care, all children accessing insulin pumps irrespective of the pathway to access it, will have extensive support from their diabetes clinical team in regard to management and ongoing access of pump following the 4-year warranty life of their pump, should they wish to continue with this therapy.

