### **4.3 Source and Selection of Participants**

**Contemporary Cohort:** All eligible children and adolescents with newly diagnosed T1D between 1st April 2024 to 31st March 2025 under the care of the diabetes service at PCH will be invited to be recruited in the study. Within this cohort, all eligible patients are to be offered AHCL as per the previously outlined model of care and initiated on AHCL within 12 weeks. Consent for participation in the study will be taken by the research fellow (or in their absence, a member of the research team) who is not involved in routine clinical care of the patient. This will occur during their scheduled Newly Diagnosed Clinic appointments rather than at an additional study visit. It will be made clear to those approached and their families that their routine clinical care will not be impacted by declining study participation.

**Historical Cohort:** The historical comparison cohort will include those diagnosed with T1D between 1st April 2022 to 31st March 2023, prior to the change in model of care. Individuals will be identified from the WA Children's Diabetes Database (WACDD). WACDD is a clinical resource, where routine clinical data is collected, entered and stored (see section 4.7.2 and 8.6 below) for individuals with T1D undergoing clinical care at PCH. Where data relevant to the historical cohort is missing, a study investigator will retrospectively collect this data where able/applicable.

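### The historical cohort's 24-month HbA1c falls almost entirely after the apparent start of the universal AHCL offer, so the 24-month comparison is early universal access versus limited, then later, access and is probably diluted

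*Protocol*

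**What the plan says.** Protocol section 4.3 separates the cohorts by date of diagnosis only. The historical cohort is those "diagnosed with T1D between 1 st April 2022 to 31 st March 2023, prior to the change in model of care"; the contemporary cohort is those with "newly diagnosed T1D between 1 st April 2024 to 31 st March 2025". Section 8.1 gives a slightly wider historical window, "the cohort newly diagnosed between March 2022 and March 2023".

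Section 8.1 makes 24 months the main comparison ("The 24-month HbA1c in the contemporary cohort will be compared to the historical control through multivariable regression model") and calls the 6- and 12-month comparisons interim. Section 6.2 names the adjusted difference at 6, 12 and 24 months as the primary efficacy assessment. The hypothesis in section 3 counts these times from diagnosis.

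On who is offered AHCL, section 4.2 states that "AHCL will be now offered to all children with T1D within this model of care". Section 2 says the service starts AHCL after diagnosis "alongside initiating ACHL in those with an established diagnosis of T1D". Another sentence in section 2 states the study goal for newly diagnosed children only. No section gives the date on which the universal offer began.

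The analysis in section 8.1 is covariate adjustment, with an inverse-probability-of-treatment-weighted regression as sensitivity analysis. The cost-effectiveness analysis there uses the previous model of care as comparator.

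**The concern.** Diagnosis date fixes which model a child entered under. It does not keep that child under the previous model until month 24. If the new offer reaches children with established disease, historical children can start AHCL because of it before their 24-month HbA1c is taken.

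Nothing planned deals with this. Covariate adjustment and propensity weighting address differences between the cohorts in their characteristics, not treatment started during follow-up. The exploratory analysis by timing of AHCL start and the uptake proportions are descriptive and leave the main contrast as it is. The sample-size statement in section 8.2 makes no allowance for crossover.

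At stake is what a null or attenuated 24-month result can be taken to mean. It could be read as showing that early equitable access brings no lasting benefit, when part of the comparator had by then received the same offer. Comparator service-use costs late in year 2 are affected in the same way.

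**Working it through.** **Inputs.** Cohort windows: section 4.3. Times counted from diagnosis: section 3. Visit tolerance of 6 weeks (42 days) either side: section 4.7.3. Cohort size 130 to 150, difference 0.35%, power above 80%: section 8.2. Two-sided 5% level: section 8.3. Start of the universal offer: not stated; 1 April 2024 is assumed, the first day of the contemporary window. Diagnosis dates are assumed uniform over the year.

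**Step 1: calendar of the historical readings** (diagnosis date plus nominal months)

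| Time point | Nominal dates | Position relative to 1 April 2024 |
|---|---|---|
| 6 months | 1 Oct 2022 to 30 Sep 2023 | all before |
| 12 months | 1 Apr 2023 to 31 Mar 2024 | all before |
| 24 months | 1 Apr 2024 to 31 Mar 2025 | all on or after |

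With the 42-day tolerance, the earliest 24-month reading could be 19 February 2024. Up to 11.5% of the cohort could then be read before 1 April 2024, or about 2.9% if visits spread evenly over the window. Likewise about 3% of 12-month readings would fall after that date. Under the wording of section 8.1, nominal 24-month dates begin in March 2024.

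**Step 2: time under the new offer before the 24-month reading.** A child diagnosed d days after 1 April 2022 has about d days of exposure to the offer. The range is 0 to 364 days, the mean 182 days (6.0 months), and 75% have at least 90 days. Section 2 describes HbA1c as a three-month measure, so most of these children could have a full measurement period under the offer. On 1 April 2024 historical children were 12 to 24 months past diagnosis.

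**Step 3: the plan's own power figure.** Power = Φ(δ / (SD·√(2/n)) − 1.96). The SD is not given, so the stated power cannot be reproduced; it can be solved for the SD it implies, SD = 0.35 / (2.802·√(2/n)):

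- n = 130: 0.35 / (2.802 × 0.1240) = 1.01
- n = 150: 0.35 / (2.802 × 0.1155) = 1.08

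An SD of 0.8 gives 94 to 97% power, 1.0 gives 81 to 86%, 1.2 gives 65 to 71% and 1.5 gives 47 to 52%. The claim is attainable but cannot be confirmed.

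**Step 4: what dilution would cost.** Set the SD so that power at 0.35% is exactly 80%. At n = 130 the standard error is 1.007 × 0.1240 = 0.1249.

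| Shrinkage of the difference | Difference | Difference / SE | Power |
|---|---|---|---|
| 0% | 0.350 | 2.80 | 80% |
| 10% | 0.315 | 2.52 | 71% |
| 25% | 0.2625 | 2.10 | 56% |
| 50% | 0.175 | 1.40 | 29% |

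The same powers result at n = 150 with SD 1.08. The shrinkage values are illustrative, since the protocol gives no crossover rate.

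**Step 5: year-2 costs.** Year 2 for the child diagnosed at d runs from d + 12 to d + 24 months after 1 April 2022. The offer is assumed to begin at month 24, so d of those 12 months fall under it. Averaged over d from 0 to 12, this is 6 of 12, or half of the comparator's year-2 person-time.

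**The case against.** The strongest reply is that Aim 1 concerns access in the first 12 weeks, and every historical child had passed that point well before April 2024 (the last by June 2023). Each spent 12 to 24 months before the assumed offer date and at most about 12 after it. A reader might infer that the 24-month analysis no longer compares the new model with the previous one at all. The documents do not support that: the contrast is weakened, not lost.

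A reader might also infer that every historical 24-month reading follows the offer. That is true of nominal dates only. The offer date is itself an inference; section 2 speaks of the model as already implemented, so an earlier start is possible. An earlier start would lengthen exposure before the 24-month reading and could bring some 12-month readings under the offer too. Moreover, an offer is not uptake, and the narrower goal in section 2 leaves open how far established patients obtain funded pumps.

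It is tempting to put AHCL use in the historical cohort at about one third at 12 months and one half at 24 months and to derive power from that. The protocol does not support those inputs. The third rests on 45 starters recorded for 2022 up to the time of writing, and the half describes the whole clinic. Use gained through insurance, self-funding or philanthropy belongs to the previous model and is not contamination.

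Finally, section 6.2 already lists 6 and 12 months as primary, so a 24-month null would be read beside them. That lowers the severity, but it does not correct the label on the 24-month contrast. Comparator QALYs come from an external national survey and are not affected by this route; only service-use costs are.

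**Conclusion.** The point holds as a should-fix. Nearly all historical 24-month readings fall after the apparent start of an offer that sections 2 and 4.2 extend to children with established diabetes, and the plan neither acknowledges nor handles this. The 24-month result estimates early universal access against limited, then later, access. The likely bias is toward no difference, and greater for children diagnosed late in the historical window. Its size cannot be fixed from the protocol; the powers of 71%, 56% and 29% show sensitivity only and are not a forecast. The conclusion assumes that the offer began about 1 April 2024 and that some historical children took it up. On that date, the 6- and 12-month comparisons are largely unaffected.

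**What to change.** 1. In sections 3, 6.2 and 8.1, state the date on which the universal offer began. Describe the 24-month contrast as early versus limited or later access, and report the 12-month difference, already primary in section 6.2, as the comparison of the new with the previous model. Check that the stated date leaves the 12-month readings before the offer. The 24-month comparison need not be demoted; that would be a trade-off against the stated aim.
2. Tabulate AHCL use and start dates in both cohorts at 6, 12 and 24 months beside each HbA1c difference.
3. Add a 24-month sensitivity analysis that censors historical children only when they start AHCL through the new offer, with inverse-probability-of-censoring weights. Pump source, listed in section 4.7.2.3, may identify these starts; otherwise use starts after the offer date, accepting that some of those would have happened anyway. Do not censor at any AHCL start: that would remove use belonging to the previous model and turn the comparator into care without AHCL.
4. In the cost-effectiveness text of section 8.1, note that comparator service-use costs after the offer date are not purely those of the previous model.

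The cost is protocol wording, one table from device data that are largely collected already, and one further analysis. The price is a more qualified 24-month claim.

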## **8.2 Sample Size**

Over a 12-month period at PCH there are 130-150 children newly diagnosed with T1D depending on annual variation. With a similar sized historical cohort, we expect sufficient power (>80%) to detect moderate effects (greater than 0.35%) in our primary analysis.

With regard to the prospectively collected data, we expect at least 80% uptake of this study, resulting in approximately 105-121 patients to be consented to make up the contemporary cohort.

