### **4.4 Participant inclusion criteria.**

1. New Diagnosis of T1D between 1st April 2024 and 31st March 2025.
2. Age 1-17.99 years.
3. Willing to complete study questionnaires.

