### **4.5 Participant exclusion criteria.**

1. Age <1 year old (no TGA approved AHCL system for this age group).
2. Unwillingness to complete study questionnaires.
3. Does not have at least one caregiver that can read and write English for instruments that are not available in translated versions

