## **8.3 Study Power and Significance**

P values of <0.05 will be used to determine statistical significance and 2-sided P-values will be reported. Corrections for multiple comparisons will not be employed.

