## **8.5 Selection of participants for analyses**

Fully detailed in section 4.3. All participants newly diagnosed with T1D in the 12 months following study commencement along with historical controls identified from WACDD, will be included in the primary analysis.

Data for the historical cohort is available on WACDD. Parents of PCH patients and PCH patients aged over 16 years of age are provided with an information sheet and consented to have their health information recorded in the PCH component of the shared database (WACDD, HREC Ref 2013051EP), for clinical, audit and research purposes.

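### The primary HbA1c analysis set is defined two ways, and one of them filters only the contemporary cohort on questionnaire willingness and caregiver English

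*Protocol*

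**What the plan says.** **Whole-population definition.** Protocol section 8.1 equates the contemporary cohort with all children diagnosed during the year after study start and takes routine clinical data for both cohorts from WACDD. The first paragraph of section 8.2 gives 130-150 new diagnoses a year and a historical cohort of similar size, and concludes "we expect sufficient power (>80%) to detect moderate effects (greater than 0.35%) in our primary analysis".

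**Restricted definition.** Section 4.3, under its contemporary-cohort label, describes eligible children who are invited to enrol. Section 4.4 requires "Willing to complete study questionnaires", and section 4.5 excludes a child who "Does not have at least one caregiver that can read and write English", a criterion that goes on to refer to untranslated instruments. The second paragraph of section 8.2 applies at least 80% uptake, "resulting in approximately 105-121 patients to be consented to make up the contemporary cohort".

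**The section that should decide.** Section 8.5 refers to section 4.3 for full detail. It then says that all participants diagnosed in the year after study commencement, "along with historical controls identified from WACDD, will be included in the primary analysis".

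**Historical cohort.** Section 4.3 identifies these children from WACDD by date of diagnosis (1 April 2022 to 31 March 2023). The criteria in section 4.4 are dated to 2024-25 diagnoses, and no questionnaire, language or age criterion is stated for the historical group.

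**The concern.** In a before-after comparison without randomisation, the rule for who enters each cohort is the main protection against a spurious difference. Here an analyst could follow either definition and cite the protocol for it. With HbA1c comparisons planned at 6 and 12 months before the 24-month analysis, the choice could also be made after results have been seen.

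The two definitions are not equally safe. Families who agree to two years of questionnaires and read English may differ in engagement, and so in HbA1c, from those who do not. Selecting the contemporary cohort this way while leaving the historical cohort unselected could produce an apparent benefit from selection alone. Willingness to take part was never observed in the historical children, so neither the multivariable model nor the inverse-probability-weighted sensitivity analysis can balance it. Correlated sociodemographic covariates would remove only part of it.

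The restriction also cuts against the study's purpose, which is to evaluate equitable access for all children. Section 4.2 gives language barriers as an example of why closed-loop therapy might be judged unsuitable. Leaving those families out of the denominator could raise the reported device uptake as well.

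**Working it through.** **1. Which reading does each section support?**

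| Protocol section | Contemporary cohort |
|---|---|
| 8.1 | all new diagnoses, WACDD data |
| 8.2, first paragraph | 130-150, all new diagnoses |
| 8.2, second paragraph | 105-121 consented patients |
| 4.3 to 4.5 | eligible, invited, questionnaire-willing, English-literate caregiver |
| 4.6 | an enrolled child who withdraws stays in through WACDD |
| 8.5 | all participants, with detail referred to 4.3 |

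Section 4.6 covers children who enrol and later withdraw. No section says what happens to children who decline enrolment or do not meet the English criterion.

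**2. Share affected.** From section 8.2: 1 - 105/130 = 19.2% and 1 - 121/150 = 19.3%, so roughly 20% of new diagnoses fall between the two definitions.

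**3. Possible shift in the contrast.** If a share p is left out of one cohort and its mean HbA1c is g points above that of the recruited children, the cohort mean falls by p × g. The protocol gives no value for g, so 0.25 to 1.0 is assumed. The fraction is relative to the 0.35 target.

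- g = 0.25: 0.20 × 0.25 = 0.05 points (0.05/0.35 = 14%)
- g = 0.50: 0.20 × 0.50 = 0.10 points (29%)
- g = 1.00: 0.20 × 1.00 = 0.20 points (57%)

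These are unadjusted shifts. If the children not recruited had lower HbA1c, the sign would reverse.

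**4. The plan's power figure.** Section 8.3 fixes the test: "P values of <0.05 will be used to determine statistical significance and 2-sided P-values will be reported". Section 8.2 gives the difference (0.35%) and the cohort sizes but no SD, so the power figure of more than 80% cannot be reproduced from the protocol alone. The largest SD that gives 80% power (normal approximation) is

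SD_max = 0.35 / [(1.960 + 0.842) × √(1/n₁ + 1/n₂)]

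- 130 v 130: 0.35 / (2.802 × 0.1240) = 1.007
- 150 v 150: 0.35 / (2.802 × 0.1155) = 1.082
- 105 v 130: 0.35 / (2.802 × 0.1312) = 0.952
- 121 v 150: 0.35 / (2.802 × 0.1222) = 1.022

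Power for 0.35% at assumed SDs, before missing data and covariate adjustment:

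| SD | 130 v 130 | 105 v 130 | 150 v 150 | 121 v 150 |
|---|---|---|---|---|
| 0.9 | 88.0% | 84.2% | 92.0% | 88.9% |
| 1.0 | 80.6% | 76.0% | 85.8% | 81.7% |
| 1.1 | 72.8% | 67.9% | 78.7% | 74.0% |

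At SD 1.0, moving to the consented set costs 80.6 - 76.0 = 4.6 or 85.8 - 81.7 = 4.1 percentage points. Whether that crosses 80% depends on the unstated SD.

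**The case against.** The best defence is that the protocol already means the whole population. The sentence with 105-121 opens by limiting itself to data collected prospectively, so it can be read as sizing the survey component. The English criterion is tied to untranslated instruments. WACDD consent is separate and sought at diagnosis, and section 4.6 says that withdrawal affects only the survey data. Sections 8.1 and 8.5 lean the same way. This makes the whole-population reading the more likely intention, but it does not remove the conflict: section 8.2 still says that the consented patients make up the contemporary cohort, sections 4.4 and 4.5 do not confine their criteria to the survey, and section 8.5 points back to section 4.3.

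A reader might go further and infer three things that the protocol does not support.

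- **That the primary comparison is already biased.** The bias arises only under the restricted definition, its size is assumed, and adjustment would absorb some of it.
- **That the stated power fails.** It rests on 130-150 per cohort and is attainable at any SD up to about 1.0 or 1.08. Even on the restricted reading, 121 v 150 gives about 82% at SD 1.0.
- **That early starters will be tested against all historical controls.** Section 8.1 says "Subanalysis reviewing mean HbA1c on those commencing on AHCL within 12 weeks from diagnosis will similarly be examined", after exploratory analyses that present means. It states no such test.

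Nor is the historical cohort wholly unselected. WACDD holds consenting families only, so that consent applies to both cohorts.

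**Conclusion.** The primary HbA1c analysis set is stated inconsistently and needs to be fixed before outcome data are compared. The two definitions differ by roughly 20% of the contemporary cohort. Under the restricted one, only that cohort is selected on willingness and language, which could favour the new model and cannot be fully adjusted away. The illustrative shift of 0.05 to 0.20 points rests entirely on an assumed gap of 0.25 to 1.0 points in the children not recruited. A power shortfall is not shown. What can be said is that the SD behind 0.35% is missing and that 80% power needs an SD of at most about 1.0 (130 per cohort) or 1.08 (150 per cohort), before missing data and covariate adjustment.

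**What to change.** 1. **Sections 4.4 and 4.5:** state that the questionnaire-willingness and English-literacy criteria govern entry to the survey component only.
2. **Sections 4.3 and 8.5:** define the primary HbA1c set, and the denominator for device uptake, as every WACDD-consented child aged 1-17.99 years diagnosed in each cohort's window. Apply identical criteria to both cohorts, regardless of questionnaire consent or withdrawal from the survey.
3. **Section 8.2:** reword so that 105-121 refers to the survey component alone, and state the SD assumed for the 0.35% difference.

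The cost is protocol wording. The HbA1c data are routine, and according to sections 4.7.2.1 and 8.5 WACDD consent is sought at diagnosis and covers research use, so no new data collection is needed. If the whole population was always intended, the change only confirms it.
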